9.2.1 Primary

The primary endpoint is knowledge levels of key information included in the ENJAYMO™ Physician's Guide across these 4 domains (assessed by 6 questions):

- Indication for CAD patients only (question 3)
- Important potential risks of serious infections including meningococcal infections (questions 4 and 6)
- Recommendations for vaccination of patients as per local regulations (question 5)
- Recommendations for monitoring and counseling patients to promote real-world safe-use conditions (questions 7 and 8).

The primary endpoint is a composite endpoint based on the percentages of HCPs with correct responses to questions included in the composite. The composite is the weighted average knowledge level across the core question set (6 questions) from the above domains. Success

criteria for the primary endpoint percentage is at least 80% of HCPs have answered the item correctly (if the number of HCPs who answered is at least 30).

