9.7 Study Size

A sample of 50 completed surveys is targeted for this study, with possibly 10 of the HCPs having actually prescribed ENJAYMO™ (this number depends on uptake of ENJAYMO™ and is very difficult to predict). Although reasonable efforts will be made to reach the target, the actual sample size will depend on actual prescribing of ENJAYMO™ as well as HCPs' willingness to participate. The sample size was determined based on both feasibility and statistical considerations, giving the rarity of CAD and therefore anticipated low number of actual ENJAYMO™ prescribers.

A recent meta-analysis of data from 23 HCP surveys found the proportions of HCPs who completed a survey among those invited ranged from 0.5% to 26.0%, with a pooled estimated proportion of 2.1% (95% confidence interval [CI]: 2.1-2.2) based on a fixed effects model, or 4.7% (95% CI: 3.0-6.6) based on a random effects model(4). Based on this plus the ICON's anecdotal experience with similar surveys, this survey estimates that a response rate of 5% is achievable. Based on this estimated response rate, at least 1,000 HCPs may need to be contacted to obtain 50 completed surveys.

Error! Reference source not found. below provides the precision and 2-sided 95% CI for different assumptions regarding levels of knowledge and number of completed surveys for this study. The primary evaluation criteria is the composite weighted average knowledge levels for the core question set. With a response from 50 HCPs and an observed knowledge level of 80%, the true value would be estimated to lie within the margin of 68.9-91.1% (i.e. with a precision of 11.1%).

Table 9-3: Precision and 95% Confidence Intervals for Various Combinations of Sample Size and Knowledge Levels

Sample Size	Probable Respondent Knowledge Levels							
	60%		70%		80%		90%	
	Precision (%)	95% CI	Precision (%)	95% CI	Precision (%)	95% CI	Precision (%)	95% CI
25	19.2	40.8, 79.2	18.0	52.0, 88.0	15.7	64.3, 95.7	10.9	78.2, 100.0
50	13.6	46.4, 73.6	12.7	57.3, 82.7	11.1	68.9, 91.1	8.3	81.7, 98.3
75	11.1	48.9, 71.1	10.4	59.6, 80.4	9.1	70.9, 89.1	6.8	83.2, 96.8
100	9.6	50.4, 69.6	9.0	61.0, 79.0	7.8	72.2, 87.8	5.9	84.1, 95.9

Note: Calculated using PASS 12 software,* confidence intervals for 1 proportion, simple asymptotic formula.

* Hintze, J. (2014). PASS 12. NCSS, LLC. Kaysville, Utah, USA. www.ncss.com.

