9.9.1.2 Statistical Methods

Data analysis will be performed by ICON qualified personnel in accordance with ICON's SOPs for statistical analysis and programming. All analyses will be performed using appropriate statistical software (e.g., SAS[®] Version 9.0 or later). A report summarising the results of the survey will be developed.

The primary criteria is the composite knowledge level for the core question set. The composite will be an opportunity/denominator based weighted percentage of HCPs who have answered each item correctly (if at least 30 HCPs have completed the item).

Other criteria include measures of receipt and reading of the ENJAYMO™ Physician's Guide, knowledge levels for each question regarding the information included in the ENJAYMO™ Physician's Guide (i.e., all questions relating to all domains), assessed as the percentages of HCPs with correct responses to each question, the distribution of HCPs' responses regarding their experience with patients' receptivity to vaccination and the implementation of vaccination (date of vaccination versus treatment start, if the prescriber administered the vaccinations), and the distribution of responses regarding the primary source(s) from which HCPs learned about the information included in the ENJAYMO™ Physician's Guide.

Descriptive data analyses will be conducted for all primary and secondary objectives. Descriptive statistics for continuous data will include N, means, and standard deviations. Results for some continuous variables may include ranges (minimums and maximums) and medians as well. Categorical data will be summarised using frequency counts and percentages. Knowledge levels will be calculated with 95% 2-sided CI. Knowledge levels will also be stratified by items with potential to confound the knowledge level (e.g., country, specialty, reads/uses vs. did not read/does not use the ENJAYMO™ Physician's Guide,

prescribing status). Missing data will be reported, but no replacement or imputation will be performed.

For each primary endpoint, the weighted average percentage of HCPs who answered the core question set correctly will be estimated and assessed against the 80% (\pm 95% CI) target (if the number of HCPs who answered the item is at least 30).

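### The protocol states two inconsistent decision rules for the primary endpoint: at least 80%, and an 80% target that carries its own confidence interval

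*Protocol*

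**What the plan says.** Four places in the protocol bear on how the primary result is judged.

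- Section 9.2.1, and the synopsis under Variables, give the only text labelled as success criteria: "criteria for the primary endpoint percentage is at least 80% of HCPs have answered the item correctly". There is no allowance for sampling error.
- Section 9.9.1.2, and the synopsis under Data Analysis, say that the weighted average "will be estimated and assessed against the 80% (\pm 95% CI) target". Neither says whether the point estimate, the lower limit or the upper limit decides.

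Both wordings are conditional on a minimum number of respondents; in section 9.9.1.2 it reads "if the number of HCPs who answered the item is at least 30". Section 9.9.1.2 also states, separately, "Knowledge levels will be calculated with 95% 2-sided CI". Section 9.7 sets the planned size: "A sample of 50 completed surveys is targeted for this study". The formula under Table 9-3 is described as "confidence intervals for 1 proportion, simple asymptotic formula". Section 8.2 says that the study has no prior hypothesis.

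**The concern.** A target is a fixed number and has no confidence interval; the estimate does. Attaching the interval to the 80% invites a tolerance reading, in which a result that sampling error could separate from 80% is on target. That would be success by non-significance, and its bar drops as the number of respondents drops.

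Sections 9.2.1 and 9.9.1.2 can then give opposite answers for the same data. An observed 70% from 50 respondents fails the plain rule and passes the tolerance reading. The study judges a risk minimisation measure for serious infections, so the rule that decides should be unambiguous before results are seen. This is not a detail that can simply be left to the SAP: the protocol itself states both the criterion and the assessment, and they differ.

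**Working it through.** **Inputs.** Threshold 80% (9.2.1, 9.9.1.2). Two-sided 95% interval (9.9.1.2). Planned n = 50 (9.7); smallest n at which the assessment is made, 30 (9.2.1, 9.9.1.2). Simple asymptotic interval for one proportion (note to Table 9-3). True knowledge of 70% is one of the levels tabulated in Table 9-3.

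**Step 1: reproduce the plan's figure.** Half-width = 1.96 × √(p(1 − p)/n). At p = 0.80 and n = 50: 1.96 × √(0.16/50) = 0.1109, or 11.1 points, giving 68.9 to 91.1%. This agrees with section 9.7: "the true value would be estimated to lie within the margin of 68.9-91.1% (i.e. with a precision of 11.1%)". At n = 30 the half-width is 1.96 × √(0.16/30) = 0.143, or 14.3 points.

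**Step 2: three rules and the lowest result that passes each.**

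- *Plain rule* (9.2.1): observed proportion at least 80%. This needs 40/50 or 24/30.
- *Fixed band*: observed proportion at least 80% minus the half-width at 80%. The lower edges are 68.9% and 65.7%, so it needs 35/50 (70.0%) or 20/30 (66.7%).
- *Interval overlap*: upper limit of the interval around the estimate reaches 80%. For 34/50: 0.68 + 1.96 × √(0.68 × 0.32/50) = 0.809, pass. For 33/50: 0.66 + 1.96 × √(0.66 × 0.34/50) = 0.791, fail. For 19/30: 0.633 + 1.96 × √(0.633 × 0.367/30) = 0.806, pass. For 18/30: 0.775, fail.

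Under overlap the lowest passing result is 72/100 (72.0%), 53/75 (70.7%), 34/50 (68.0%) and 19/30 (63.3%), so the bar falls as n falls. For the band, only the lower edge is applied here.

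**Step 3: chance of passing, P(X ≥ r) with X binomial(n, true level).**

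| True level | n | Plain rule | Fixed band | Interval overlap |
|---|---|---|---|---|
| 60% | 50 | 0.2% | 10% | 16% |
| 65% | 50 | 2% | 28% | 39% |
| 70% | 50 | 8% | 57% | 68% |
| 75% | 50 | 26% | 84% | 90% |
| 70% | 30 | 16% | 73% | 84% |
| 75% | 30 | 35% | 89% | 95% |

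At true 70% and n = 50, the plain and overlap rules differ by 68 − 8 = 60 percentage points.

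**Step 4: the composite.** The primary endpoint averages six questions, so Step 3 is a guide and not its exact behaviour. Beta-binomial simulation of six answers per respondent, with within-respondent correlation from 0 to 0.5 (an assumption; the protocol gives none), gives these overlap pass rates at true 70%, n = 50:

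- interval based on the number of respondents, as in Table 9-3: 74 to 89%;
- interval using the between-respondent variance of the six-item score (clustered): 3 to 49%;
- interval treating all 6n answers as independent: 3 to 15%.

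The plain rule passes in 0 to 2%.

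**The case against.** The protocol nowhere says that an interval reaching 80% is success. The text labelled as success criteria allows no tolerance, and section 9.9.1.2 attaches the interval to the estimate in its own sentence on knowledge levels. Read together, the intent may simply be to compare the estimate with 80% and report its interval. A literal two-sided band would even put an observed 95% at n = 50 outside 68.9 to 91.1%, which suggests loose drafting. This stands: the tolerance rule is one possible reading, not a rule that the protocol fixes.

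A reader might go further and infer that clearly inadequate knowledge would usually be passed. The documents do not support that. It needs a tolerance reading; at n = 50 it also needs a single-proportion interval, which section 9.7 uses for sizing and does not prescribe for analysing the composite. With a clustered interval, passing at true 70% and n = 50 is a minority outcome. Even on the single-proportion basis, true 65% passes 39% of the time at n = 50. Nor does the protocol define 70% as inadequate.

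A reader might also fault the plain rule because it is met 58% of the time at n = 50 when true knowledge is exactly 80%. That is inherent in any point-estimate benchmark, and acceptable in a descriptive study with no prior hypothesis.

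Finally, low response is not left unchecked: assessment needs at least 30 respondents, fewer than 30 completed surveys triggers a second wave (9.3), and recruitment does not close early on reaching 50 (9.1.1). None of this removes the conflict between the two wordings.

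**Conclusion.** Wrong as written. The protocol gives two wordings of the decision rule that do not agree, and one misplaces the interval. On a single-proportion basis with the Table 9-3 formula, true knowledge of 70% passes 57 to 68% of the time at n = 50 and 73 to 84% at n = 30 under the tolerance readings, against 8% and 16% under the plain rule.

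These figures assume independent respondents and that the tolerance reading is adopted. For the composite, the size of the gap depends on how its interval is built and on the assumed within-respondent correlation: with a clustered interval, overlap passes in roughly 3 to 49% at n = 50, still above the plain rule's 0 to 2%. The finding is an inconsistent rule whose wording permits a weak standard, not proof that the weak standard will be applied.

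**What to change.** In section 9.9.1.2 and the synopsis (Data Analysis), delete the parenthesis after 80% and state the rule of section 9.2.1 and the synopsis (Variables): the target is met if the composite point estimate is at least 80%, reported with its two-sided 95% confidence interval. Add that an interval merely including 80% does not count as success.

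Reporting whether the lower 95% limit also reaches 80% is optional. On a single-proportion basis at n = 50 that needs 45/50, since 0.90 − 1.96 × √(0.90 × 0.10/50) = 0.817, whereas 44/50 gives 0.790. It should not become the success criterion without revisiting the sample size: at true knowledge of 90% and n = 50, the lower limit reaches 80% in only 62% of surveys.

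The cost is wording in the protocol, carried into the SAP. No extra data or respondents are needed.

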9.10 Quality Control

ICON is responsible for following their SOPs as well as Sanofi' SOPs whenever appropriate to ensure data quality and integrity, including archiving of statistical programmes, appropriate documentation of data cleaning and validation of derived variables, and description of available data.

9.11 Limitations of the Research Methods

A primary limitation of this cross-sectional survey is potential selection bias due to use of a convenience sample and/or low response rates. Moreover, the rarity of CAD and the relatively recent approval (meaning reimbursement in many EU countries may not yet or may only recently be available) may compromise the ability to identify a sufficiently large number of ENJAYMO™ prescribers to complete the survey. Therefore, the survey will be conducted amongst HCPs who treat CAD and were sent the ENJAYMO™ Physician's Guide, rather than limiting the survey to only ENJAYMO™ prescribers. Analyses will be performed stratified by ENJAYMO™ prescribing status.

The impact of selection bias can be minimized through robust outreach to recruit a representative sample of HCPs who have received the ENJAYMO™ Physician's Guide. For this survey, to minimize selection bias, HCPs from a broadly representative sample of European countries, geographically and via market-share, will be invited to participate. Countries in the EEA where the product is expected to be commercially available for at least 6 months may be included.

Generalizability of the study results may be limited in that the study population is based on a convenience sample. To improve generalizability, all HCP potential prescribers from included countries who were sent the ENJAYMO™ Physician's Guide, will be invited to participate in the survey (where sharing HCP contact information is allowed/available). To further endeavor to minimize selection bias:

- HCPs who have not responded will receive up to two reminders to encourage their participation.
- The HCP eligibility criteria are limited to target a broad population of HCPs available to prescribe ENJAYMO™.
- Where appropriate, HCPs will be offered a small reimbursement, based on FMV, for their time to complete the survey.

- Where HCPs are not able to commit to completing the survey, they will be provided the option to respond to one question indicating their reason for not participating in the survey.

Another limitation is reliance on self-reporting which can result in social desirability reporting bias(5). In a web-based survey of 3625 HCPs across 9 EU countries conducted under the Strengthening Collaborations for Operating Pharmacovigilance in Europe (SCOPE) joint action initiative, a range from 28% to 97% of HCPs reported receiving and sometimes reading risk communication materials. Given the results were not uniformly high, this survey suggested that HCPs may be comfortable providing truthful responses to this type of question (even if possibly “socially undesirable”)(6, 7). Recall bias can also impact study results, e.g. if there is a long lag time between the distribution of the ENJAYMO™ Physician’s Guide and completing this survey. This will be assessed by stratifying the primary endpoint analyses by duration between distribution of the Physician’s Guide and completion of the survey.

Some survey items, such as those assessing HCPs’ experience with patients’ receptivity to vaccination and implementation of vaccination (date of vaccinations versus treatment start, if the prescriber administered the vaccinations), are only answerable by HCPs who have prescribed ENJAYMO™. Depending on the distribution of prescribers vs. non-prescribers in the survey, the number of responses may be low for these items, decreasing the precision of this secondary endpoint.

10 PROTECTION OF HUMAN PATIENTS

Although there are no patients in this study, the HCPs are research subjects. As such, this study will be conducted in compliance with national and EU requirements for ensuring the rights of participants in non-interventional studies.

10.1 Institutional Review Board (IRB) / Independent Ethics Committee (IEC) / Competent Authorities (CA)

It is the responsibility of ICON to have prospective approval of the study protocol, protocol amendments, and other relevant documents (e.g., recruitment advertisements), if applicable, from the independent ethics committees (IEC). Where applicable, all correspondence with the IEC will be retained in ICON’s study-specific file.

10.2 Ethical Conduct of the Study

The study will be conducted in accordance with legal and regulatory requirements, as well as with scientific purpose, value, and rigour and follow generally accepted research practices described in Good Pharmacoepidemiology Practice issued by the International Society for Pharmacoepidemiology (ISPE), the EMA European Network of Centres for

Pharmacoepidemiology and Pharmacovigilance (ENCePP) Guide on Methodological Standards in Pharmacoepidemiology, and GVP Module VIII – post-authorisation safety studies.

10.3 Patient Information and Consent

Although there are no patients in this study, the HCPs are considered study subjects. Survey participants will be asked to provide acknowledgement of consent to participate in the survey as part of the on-line consulting agreement completed by HCPs prior to accessing the survey.

10.4 Patient Confidentiality

Although there are no patients in this study, the HCPs are considered study subjects. HCPs' survey responses will be reported in aggregate and de-identified. Data will be stored in a secure validated database and shall be treated in compliance with all local applicable laws and regulations.

11 MANAGEMENT AND REPORTING OF ADVERSE EVENTS/ADVERSE REACTIONS

11.1 Primary Data Collection

This direct-to-HCP survey does not involve patient-specific data collection and does not involve exposure to a study drug. In this survey, HCPs are the research subjects and will complete an online survey to assess knowledge via a secure website. The online survey does not include questions that could potentially identify an adverse event (AE).

However, during survey conduct, an HCP may provide unsolicited information to study personnel that could constitute an AE (e.g., while seeking information about the purpose of the survey). Since this would occur under a study, it would be considered as a solicited report.

In the event that an HCP survey participant reports an AE associated with the use of ENJAYMO™, ICON will complete an AE report form and submit it to Sanofi immediately (within 24 hours of awareness) for serious adverse events (SAEs), while non-serious AEs will be reported within 30 days of awareness. Included in the completion of the AE report form is the HCP's contact information as the reporter. Complete contact information should be obtained so that, once the AE report form is transferred to Sanofi, it can be assessed and processed according to Sanofi SOPs, including requests for follow-up regarding the AE to the HCP survey participant. As this study is not designed to collect AEs reports, additional details regarding procedures to follow in case an unanticipated AEs report is received will be included in the study-specific survey manual.

11.2 Definitions

11.2.1 Definitions of Adverse Events

An AE is defined as any untoward medical occurrence in a subject administered a study drug, and which does not necessarily have to have a causal relationship with this treatment. An AE can therefore be any unfavorable and unintended sign (including an abnormal laboratory finding), symptom, or disease (new or exacerbated) temporally associated with the use of a medicinal product whether or not considered related to the medicinal (investigational) product.

An abnormality identified during a medical test is defined as an AE per the following criteria:

- Any abnormal laboratory test result (e.g., haematology, clinical chemistry, or urinalysis) or other safety assessment (e.g., electrocardiograms, radiographic scans, vital signs measurements, physical examination), including those that worsen from baseline, that is considered to be clinically significant in the medical and scientific judgment of the investigator and not related to underlying disease, is to be reported as an (S)AE.
- Any clinically significant abnormal laboratory finding or other abnormal safety assessment which is associated with the underlying disease does not require reporting as an (S)AE, unless judged by the investigator to be more severe than expected for the subject's condition.
- Repeating an abnormal laboratory test or other safety assessment, in the absence of any of the above criteria, does not constitute an AE. Any abnormal test result that is determined to be an error does not require reporting as an AE.

11.2.2 Definitions of Adverse Drug Reaction

An Adverse Drug Reaction is defined as 'Any noxious and unintended response associated with the use of a drug in humans, at any dose, where a causal relationship (drug-event) is at least a reasonable possibility'.

11.2.3 Definitions of Serious Adverse Events (SAEs)

An adverse event is considered serious if, in the view of either the Investigator or Sponsor, it results in any of the following outcomes:

- Results in death,
- Is life threatening (an adverse event is considered "life-threatening" if, in the view of either the Investigator or Sponsor, its occurrence places the patient at immediate risk of death. It does not include an adverse event that, had it occurred in a more severe form, might have caused death),
- Results in persistent or significant disability/incapacity or substantial disruption of the ability to conduct normal life functions,
- Results in congenital anomaly, or birth defect,

- Requires inpatient hospitalisation or leads to prolongation of hospitalisation (hospitalisation for treatment/observation/examination caused by AE is to be considered as serious), or
- Other medically important events.

Medical and scientific judgment should be exercised in deciding whether expedited reporting is appropriate in other situations, such as important medical events that may not be immediately life-threatening or result in death or hospitalisation but may jeopardise the patient or may require intervention to prevent one of the other outcomes listed in the definition above. These events, including those that may result in disability/incapacity, should also usually be considered serious. Examples of such events are intensive treatment in an emergency room or at home for allergic bronchospasm; blood dyscrasias or convulsions that do not result in hospitalisation; or development of drug dependency or drug abuse.

The Sponsor has a list of events that they classify as “always serious” events. If an adverse event is reported that is considered to be an event per this classification as “always serious”, additional information on the event may be requested.

